
A.4. Circadian Rhythms are Critical to Maintain the Intestinal Barrier. Intestinal barrier homeostasis is mediated by cross-talk between IECs and the intestinal microbiota. This cross-talk occurs via multiple mechanisms including interactions with toll-like receptors (TLRs) on the IECs. There are multiple lines of evidence in cell lines, animal models, and human studies that support the scientific premise that disruption of circadian rhythms in the host negatively impacts intestinal barrier integrity: (1) alcohol (0.2%) increases the expression of the circadian clock genes Clock and Per2 in a human IEC line (Caco-2 cells), and knock down of Clock or Per2 gene expression by siRNA prevents alcohol-induced barrier dysfunction, (2) chronic disruption of the central clock by either disruption of light:dark cycles or a mutation in the core circadian molecular clock (i.e., Clock mutant mice) increases intestinal permeability and endotoxemia, (3) healthy night workers who consume alcohol (0.5g/kg daily for 7 days) have increased colonic permeability compared to healthy day workers consuming alcohol, and colonic permeability inversely correlates with decreased plasma melatonin over 24h, (4) our lab and others show that circadian misalignment in the host causes microbial alterations with a decrease in bacteria (Firmicutes) that produce short chain fatty acids (SCFA) like butyrate (Bu), and (5) the core clock machinery (Bmal1) regulates IEC cell regeneration and barrier homeostasis. Taken together, these studies strongly support the concept that circadian misalignment could promote IBD flare via a mechanism involving disrupting the colonic barrier and intestinal microbiota dysbiosis.

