**Sample Size Analysis:** All power estimates were computed using R package pwr, and we assume a Type I error rate of 0.05 and a 2-sided test for all analyses. Power estimates were derived from the data from my prior K grant. The primary endpoints of this study will be phase angle/DLMO (Aim 1) and colonic permeability (13-24h urinary sucralose) (Aim 2). For Aim 1, we found a  $\sim 2$ h phase advance in DLMO in NW compared to DW at -0.2 (SD=2.1) compared to -4.34 (SD=3.8), respectively. With a sample size of 20 in each group (10 men/10 women), this

provides an 86% power to detect differences in DLMO, but 98% power if sex is pooled. For Aim 2, we found a 40% increase in colonic permeability in night shift workers compared to day workers after moderate alcohol consumption at 0.57 compared to 0.11 (SD=0.20). With 20 subjects, this will give us a 84% power to detect a difference in colonic permeability between the two groups for each sex and if sex is pooled will give us a 97% power with a two-sided two-sample t-test at alpha=0.05 level. These conservative estimates provide a good estimate of the power to detect differences in phase angle and colonic permeability between UC patients before and after simulated night shifts. We anticipate we will have nonparametric data and will use the Wilcoxon match-pair test for analysis of colonic permeability, inflammatory cytokines, and markers of endotoxemia. Order effects will be used as a covariate in multivariate analysis with analysis of variance (ANOVA) and linear regression as indicated. Microbiota data analysis is described above. Non-parametric analysis of actigraphy data will be analyzed with the nparACT package. In our periodogram analysis of time series data we will use Fast Fourier Transform Non-linear Least Squares (FFT-NLLS), a nonlinear least-squares algorithm of a times series typically used for luminescence data (149) and analyzed with Biodare software (150). Data will be presented as mean  $\pm$  SEM for variables that can be considered normally distributed (or median and range for variables not normally distributed). All analyses will use R (v.3.2.5), Biodare 2, and SPSS (SPSS Inc., Chicago, IL).

**Inclusion Criteria:** *Study will include individuals that are;*

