liver function test], and PT. At first blood draw on Day 2 and last blood draw on Day 7, an additional 10 ml will be collected from patients on biologics, to evaluate antibody levels.

All subjects will complete an IBDQ, FFQ, BDI, STAI, PSQ, Munich Chronotype, IRLS, Demographic Questionnaire, Mayo Score, CSD-C (Consensus Sleep Diary), and Berlin Questionnaire. All information collected from subjects will be used for research purposes only. All the procedures in the study (blood draw, stool samples, urine samples, sigmoidoscopy with biopsies and questionnaires) are well-established and considered routine tests in clinical practice (including flexible sigmoidoscopy).

Diet Assessments: Meal habits will be recorded during screening. All subjects must eat breakfast (>200 kcal) at least 5 days a week, and subjects unusual diets by FFQ (vegan or gluten free) will be excluded due to impact on microbiota. For two weeks prior to each inpatient laboratory stay, all subjects will undergo ambulatory monitoring of their general activity using a small wrist activity monitor for ensuring compliance with the sleep-wake schedule. In addition, subjects will be provided meals for the last 3 days before admission and asked to keep regular meal schedules. Medical and psychiatric condition summary. Volunteers must be ambulatory and have no major visual or auditory handicaps. Medical suitability will be determined by clinical history, physical examination, and clinical biochemical screening tests of blood and urine, past or present psychopathology. Finally, a clinical interview will be carried out on all potential subjects to determine their suitability for the study and their ability to tolerate the conditions of the simulated night shifts environment (with regular contact with research staff and technicians). All volunteers selected must be drug-free with only moderate or no use of caffeine, alcohol, or other compounds by history, which will be verified during the screening process by comprehensive toxic analysis. Caffeine, alcohol, or other compounds (including herbal medications/remedies) will not be permitted for three weeks immediately prior to admission to the Clinical Chronobiology Center (CCC), and a urinary comprehensive toxic analysis will be carried out upon admission to ensure compliance. Prescribed medications are also prohibited with some exceptions.

[figure not shown]

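### The Aim 2 power of 84%/97% comes from an alcohol-exposed comparison of night and day workers, so it is unsupported, and its conservative label unexplained, for UC patients before and after simulated night shifts

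*Combined protocol and SAP*

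**What the plan says.** The Sample Size Analysis names urinary sucralose (colonic permeability) as the primary endpoint for Aim 2. Its general setting is "we assume a Type I error rate of 0.05 and a 2-sided test for all analyses". The Aim 2 effect is described as "we found a 40% increase in colonic permeability in night shift workers compared to day workers after moderate alcohol consumption", with values "at 0.57 compared to 0.11 (SD=0.20". The power statement is "With 20 subjects, this will give us a 84% power to detect a difference in colonic permeability between the two groups for each sex", rising to 97% with the sexes pooled, by a two-sided two-sample t-test. The section then transfers the result to a different contrast, the change within patients across the simulated shifts: "These conservative estimates provide a good estimate of the power to detect differences in phase angle and colonic permeability between UC patients".

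Other sections describe the setting of this trial:

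- Background A.4 reports evidence of the same kind: "healthy night workers who consume alcohol (0.5g/kg daily for 7 days) have increased colonic permeability compared to healthy day workers consuming alcohol".
- Diet Assessments, under Procedures: "Caffeine, alcohol, or other compounds (including herbal medications/remedies) will not be permitted for three weeks immediately prior to admission", with a urine toxicology check on admission. The in-lab procedures include no alcohol challenge.
- Exclusion Criteria: shift work in the previous six months rules out both UC patients and healthy controls.
- Research Design and Procedures: the UC patients have inactive disease, and every subject is measured at baseline and again after three simulated night shifts.

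**The concern.** A power statement answers a question about one contrast, in one population, under one exposure. Here the effect size was measured between two groups of workers who had consumed alcohol, and it is applied to a within-patient change in UC without alcohol. Exposure, population and comparison all differ, and no bridging figure is given. The label *conservative* asserts a direction (true power at least as high as stated) for which the section offers no argument.

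Sucralose permeability is a primary outcome. A reader who accepts 84% to 97% as a lower bound could take a null result as strong evidence against the hypothesis. The documents do not allow that inference, because they never state how large a change the trial was expected to see under its own conditions.

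**Working it through.** **Inputs (Sample Size Analysis).** Means 0.57 and 0.11; SD 0.20, taken as common to both groups; two-sided alpha 0.05. The group size is given under Aim 1: "With a sample size of 20 in each group (10 men/10 women". Hence 20 per group pooled and 10 per group within each sex.

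**1. Reproducing the plan's figure.** Standardised difference d = (0.57 − 0.11)/0.20 = 0.46/0.20 = 2.30. Two-sample t-test power uses the noncentral t with 2n − 2 degrees of freedom and noncentrality d√(n/2).

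| n per group | Noncentrality | Power from printed inputs | Stated |
|---|---|---|---|
| 10 | 2.30 × √5 = 5.14 | 99.8% | 84% |
| 20 | 2.30 × √10 = 7.27 | >99.9% | 97% |

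The stated figures do not reproduce. Solving backwards, 84% at n = 10 needs d = 1.40, and 97% at n = 20 needs d = 1.25. The two stated powers therefore do not point exactly to one effect, and neither value is 2.30.

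The printed effect is also inconsistent with its description. The rise from 0.11 to 0.57 is 0.46/0.11 = 418%, not 40%. A 40% rise on 0.11 is 0.044, so d = 0.044/0.20 = 0.22, which gives two-sample power of 7.5% (n = 10) and 10.4% (n = 20).

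**2. Source contrast and trial contrast.**

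| Element | Source of the effect | This trial |
|---|---|---|
| Alcohol | After moderate consumption | Barred for three weeks before admission |
| Exposure | Night work against day work | Three simulated night shifts; recent shift workers excluded |
| Population | Night and day workers | Inactive UC (with matched controls) |
| Comparison | Two independent groups | Same patient, before and after |
| Variance | SD 0.20, one value | No UC SD and no SD of paired change reported |

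**3. Can a correct power be computed?** No, because the needed inputs are absent. To show the spread, assume SD 0.20 at each occasion and within-patient correlation ρ of 0 or 0.5. The SD of the change is 0.20√(2(1 − ρ)), which is 0.283 or 0.200. Paired t-test power in 20 UC patients, for an assumed share of the printed difference:

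| Difference | ρ = 0 | ρ = 0.5 | Two-sample, 20 per group |
|---|---|---|---|
| 0.46 (all) | >99.9% | >99.9% | >99.9% |
| 0.23 (half) | 93% | 99.8% | 94% |
| 0.115 (quarter) | 41% | 68% | 43% |
| 0.044 (40% of 0.11) | 10% | about 16% | 10% |

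The plausible range runs from far below the stated 97% to above it.

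**4. What the design can detect.** Solving the same power functions for 80%:

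| Completers per group | Paired change within UC | Between two groups |
|---|---|---|
| 20 | 0.66 SD of the change | 0.91 SD |
| 14 | 0.81 SD of the change | 1.10 SD |

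The 14 is 0.70 × 20, from the 70% completion among those passing screening that Subject Recruitment reports; it applies if 20 means enrolled. These are t-test values. The planned tests are rank tests (matched-pair Wilcoxon in the Sample Size Analysis, Mann-Whitney U in Figure 1, Outcome Measures), for which the detectable differences are slightly larger.

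**The case against.** The best defence is that proxy data are normal in a first study of its kind, and that several changes could raise the effect or the power. The protocol hypothesises that UC patients are less resilient. Procedures chooses a 12-hour inversion because misalignment effects are said to be greatest there. Background A.6 claims supporting barrier data in UC. For the same difference and SD, a paired analysis gains power once the within-patient correlation is appreciably positive, which could be what *conservative* was meant to convey.

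Most of this stands, and it limits the point. A reader might infer that removing alcohol must shrink the effect, so that true power is below 84%/97%. The documents do not support that, since population, exposure and pairing change at the same time: half the printed difference still gives 93% to 99.8% paired power under the assumptions above. A reader might also scale down the effects implied by the stated powers. Halving d = 1.25 gives about 48% two-sample power with 20 per group, against 94% from halving the printed 2.30. The answer depends on which inconsistent input is used, so such figures should not be quoted as the trial's power.

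Two further inferences go too far. The documents fail to report an alcohol-free pilot effect; they do not show that none exists. And the Sample Size Analysis cites no study, so identifying its data with the seven-day alcohol evidence in Background A.4 is reasonable but unconfirmed.

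The defence does not supply a basis for the label. The section gives no reason for it, and the UC data mentioned elsewhere come without an effect size or SD and are not used for power.

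**Conclusion.** The point holds as a lack of support, not as a demonstrated shortfall. The 84%/97% describes a two-group, alcohol-exposed contrast in workers and is not the power of the paired, alcohol-free UC contrast to which it is applied. *Conservative* has no stated basis, and the direction of the error is unknown. Separately, the figures do not follow from the printed inputs, which give 99.8% and over 99.9%.

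What can be stated firmly is the detectable difference with 80% power: 0.66 SD of the paired change in 20 UC completers and 0.91 SD between groups of 20. This rests on t-tests, two-sided alpha 0.05 and full completion. The range in step 3 of the working rests on an assumed SD of 0.20 at each occasion and assumed correlations of 0 and 0.5. The alcohol ban is written for the three weeks before admission; that the in-lab days are also alcohol-free is read from the absence of any alcohol in the procedures.

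**What to change.** In the Sample Size Analysis, for Aim 2:

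1. Delete the 84%/97% claim and the word *conservative*.
2. State what is detectable with 80% power: 0.66 SD of the paired change in 20 UC completers and 0.91 SD between groups of 20. Note that these are t-test values, slightly larger for the planned rank tests, and that they become 0.81 and 1.10 SD if 14 per group complete.
3. Say that the protocol reports no alcohol-free effect size. If the sponsor holds one, cite it with the SD of the paired change and compute power for the planned paired test from it.
4. If the worker data stay as background, reconcile the 40% increase with 0.57 against 0.11.

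This is a text change only, with no effect on enrolment or procedures. The cost is a less favourable stated figure.

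### The sample-size paragraph's stated effects (40%, about 2 h) do not match its printed means (+418%, 4.14 h), and the Aim 2 power of 84%/97% cannot be reproduced from the one SD given

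*Combined protocol and SAP*

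**What the plan says.** All of this stands in one paragraph, the Sample Size Analysis section of the combined protocol and SAP.

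- **General:** the calculations used the R package pwr, and "we assume a Type I error rate of 0.05 and a 2-sided test for all analyses". On the source: "Power estimates were derived from the data from my prior K grant".
- **Aim 1 (phase angle/DLMO):** the effect is described as roughly a 2 h "phase advance in DLMO in NW compared to DW at -0.2 (SD=2.1) compared to -4.34 (SD=3.8), respectively". For 20 per group, split equally by sex, the design "provides an 86% power to detect differences in DLMO, but 98% power if sex is pooled".
- **Aim 2 (colonic permeability):** the effect is a "40% increase in colonic permeability in night shift workers compared to day workers after moderate alcohol consumption at 0.57 compared to 0.11 (SD=0.20"). The sample is given only as 20 subjects. By sex, the plan says "this will give us a 84% power to detect a difference in colonic permeability between the two groups for each sex". For both sexes together it adds "if sex is pooled will give us a 97% power with a two-sided two-sample t-test at alpha=0.05 level".

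Aim 1 has an SD after each mean. Aim 2 has a single SD, placed after the day-worker mean. No second SD, sex-specific input or other permeability effect appears elsewhere in the document.

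**The concern.** For each aim, the effect in words and the effect in numbers differ by a wide margin, so both cannot describe the same comparison. For Aim 2 the stated power is also far below what the printed means and SD give, although the paragraph names the test, the alpha and the software.

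These are the two primary endpoints. A reader cannot tell which effect either was powered for and cannot check the Aim 2 power at all. The choice matters: depending on which number is taken as the true prior result, power runs from near certainty to well below one half.

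**Working it through.** **Inputs (Sample Size Analysis).** Two-sided alpha 0.05; n = 10 per group within sex and 20 per group pooled. Aim 1 means -0.2 (SD 2.1) and -4.34 (SD 3.8). Aim 2 means 0.57 and 0.11, SD 0.20. *Assumptions:* means and SDs are the same in both sexes, and for Aim 2 the SD of 0.20 holds in both groups.

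**Labels (no assumption needed).**
- Aim 2: 0.57 - 0.11 = 0.46; 0.46/0.11 = 4.18, or +418%. Relative to the larger mean, 0.46/0.57 = 81%. Neither is 40%.
- Aim 1: -0.2 - (-4.34) = 4.14 h, not about 2 h.

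**Power formula.** d = difference/SD. Power is the probability that a noncentral t variable with 2n - 2 degrees of freedom and noncentrality d√(n/2) exceeds the two-sided 5% critical value.

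**Aim 1, the plan's own figure.** SD = √((2.1² + 3.8²)/2) = 3.07; d = 4.14/3.07 = 1.349.
- Exact t: 81.4% (n = 10) and 98.6% (n = 20).
- Normal approximation: 85.4% and 98.9%, close to the stated 86% and 98%.
- With 2 h instead: d = 2/3.07 = 0.651, giving 28.1% and 51.9% by exact t.

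So the stated Aim 1 power comes from the 4.14 h difference, not from 2 h.

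**Aim 2, the plan's own figure.** d = 0.46/0.20 = 2.30. The stated 84%/97% is not reproduced, and the alternative readings below miss it too.

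| Reading | Per sex | Pooled |
|---|---|---|
| Stated in the plan | 84% | 97% |
| Printed means, SD 0.20 in both groups (10 and 20 per group) | 99.8% | >99.99% |
| 20 subjects in total (5 and 10 per group) | 88.8% | 99.8% |
| 40% above 0.11 (difference 0.044, d = 0.22) | 7.5% | 10.4% |
| 40% rise ending at 0.57 (0.407 to 0.57, d = 0.814) | 40.7% | 70.9% |

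**Could a missing second SD explain it?** Take 0.20 as the day-worker SD only and assume a night-worker SD s, so that SD = √((0.20² + s²)/2).

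| Assumed s | d | Per sex | Pooled |
|---|---|---|---|
| 0.30 | 1.804 | 96.8% | 99.98% |
| 0.42 | 1.398 | 84.1% | 99.1% |
| 0.48 | 1.251 | 75.4% | 97.1% |
| 0.50 | 1.208 | 72.4% | 96.1% |

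Either stated figure can be matched this way, but not both at once to the printed rounding.

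**Implied effect sizes.** Allowing for rounding, 84% at 10 per group needs d between 1.388 and 1.407, and 97% at 20 per group needs d between 1.224 and 1.272. The ranges do not overlap, so one common d cannot give both. By exact t the Aim 1 pair also fails to share a d (86% needs 1.428 to 1.449; 98% needs 1.272 to 1.341). The mismatch there is small, and the normal approximation comes close to both figures.

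**The case against.** The best defence is that Aim 2 is incompletely reported rather than miscalculated. Aim 1 prints an SD after each mean, so the lone 0.20 after the day-worker mean may well be that group's SD, with the night-worker SD left out. An SD of 0.425 for night workers gives 83.4% and 98.9%, within two points of both stated figures. Sex-specific means and SDs could close the rest, since per-sex and pooled power then need not share one d. This stands as a possible explanation, and it is why the 99.8%/over 99.99% figures hold only under the common-SD condition. But the input it needs is printed nowhere, the match is not exact, and 40% remains unexplained.

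For Aim 1, the means look like phase angles rather than DLMO clock times. A DLMO shift of about 2 h and a phase-angle difference of 4.14 h could both be true if sleep onset also differed. The sentence, however, attaches the 2 h directly to those two means as a difference in DLMO, so the text needs correcting or clarifying either way. The 28%/52% figures apply only if the printed SDs describe the same variable as the 2 h.

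It is also fair that, with SD 0.20 common to both groups, the stated Aim 2 power errs on the low side, and that the stated Aim 1 power is roughly recoverable from its printed inputs. Neither point tells the reader which effect is real.

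**Conclusion.** The concern holds. The two label mismatches (40% against +418%; about 2 h against 4.14 h) follow from the printed means alone. The failure to reproduce the Aim 2 power is conditional: 99.8% per sex and over 99.99% pooled, against 84% and 97%, if SD 0.20 holds in both groups and both sexes. With an assumed second SD of 0.30 to 0.50, per-sex power runs from 97% to 72% and pooled power from over 99.9% to 96%. The document does not show which input is wrong or missing, so the secure conclusion is that the means, the SDs or the power figures are misreported or incomplete. The paragraph should be corrected because both primary endpoints rest on it. It does not show that the study is underpowered, and no conclusion on the adequacy of 20 per group can be drawn until the inputs are verified.

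**What to change.** Go back to the prior-grant data and revise the Sample Size Analysis section as follows:

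1. Correct the 40% and 2 h descriptions or the means, whichever is wrong. For Aim 1, say whether the values are DLMO times or phase angles.
2. Print both Aim 2 SDs, and the sex-specific means and SDs for both aims if they were used.
3. State the n per group that the reference to 20 subjects stands for.
4. Replace 84%/97% with power recomputed from the verified inputs. The values 99.8% and over 99.99% are right only if SD 0.20 is common to both groups and both sexes.
5. Make no statement on whether the sample size is adequate until this is done.

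The cost is a check of existing data and a rewrite of one paragraph. If the verified effects prove smaller than the printed means, the restated power will fall and the sample size would have to be looked at again.

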**Abstract:** Recently there has been compelling evidence that inflammatory bowel disease (IBD) subjects, both Crohn's disease (CD) and Ulcerative Colitis (UC), commonly have disrupted sleep, and disrupted sleep correlates with the risk of disease flare. Sleep/wake cycle, immune function, metabolism and multiple biological processes are all orchestrated by circadian rhythms. Circadian misalignment between the central circadian clock in the brain and environment has been found to contribute to a variety of metabolic and gastrointestinal tract (GIT) diseases. Yet, the prevalence and impact of circadian misalignment on IBD disease activity and GIT mucosal inflammation have not been established. The long-term objective of our research is to investigate the hypothesis that circadian malalignment worsens GIT mucosal inflammation and disease course in IBD. To test this hypothesis, we will conduct a prospective in lab study with human subjects on the impact of circadian misalignment in left sided mild to moderate Ulcerative Colitis. We will perform two circadian measures phase assessments under strictly controlled laboratory conditions at: 1) baseline, and after 2) circadian misalignment after three days of simulated night shifts in both inactive UC patients and healthy control subjects. To test the hypothesis that UC patients (compared to healthy subject controls) are less resilient to circadian misalignment we will assess: time impact of our protocol on circadian rhythms (Aim 1) by the following: phase angle of entrainment [time from dim light melatonin onset to sleep onset] (Aim1a); peripheral circadian rhythms by clock gene expression in colonic tissue from a flexible sigmoidoscopy and in subjects peripheral blood mononuclear cells (Aim1b); and colonic clock gene expression and Per2::Luc activity over 24 hours utilizing an in-vitro model of colonic organoids (Aim1c). Next, we will test the hypothesis that circadian misalignment will increase colonic permeability and mucosal inflammation in UC patients (vs. Controls) (Aim2) through the following: endoscopy score, stool calprotectin, colonic barrier (permeability, AJC proteins), and markers of systemic barrier function and inflammation (Aim 2a); adversely impacting microbial community structure/function (Aim 2b); and use 2D colonic organoid monolayers to explore ex-vivo barrier function by co-culturing with TNF- $\alpha$ /INF- $\gamma$  (Aim

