All experimental procedures will commence after admission to the CCC for a 7 day in-lab evaluation. The sleep episode will be the same as that maintained during the 2 weeks prior to the in-lab phase assessment. On Test Day 1 (TD1, Baseline alignment), at 0900h all subjects will have a unprepped flexible sigmoidoscopy (FS) with rectal biopsy collection (19 biopsies, ~15 cm from the anal verge), after which intestinal permeability will be assessed (24h urine collection after ingestion of a sugar cocktail: sucrose, mannitol, lactulose, sucralose103), and every 2 hour blood sampling during/surrounding standardized meals (primary and secondary outcomes for Specific Aims 1 & 2). During the last 8h of the phase assessment, subjects will be exposed to a background illumination ~3 lux to assess the endogenous circadian phase through hourly plasma melatonin (dim light melatonin onset, DLMO). On Protocol Day 3, subject behavioral cycles will be shifted by 12h, and this schedule will be maintained until Protocol Day 7. Following the short 4h sleep episode on Day 3, subjects will have 3 “night shift” days (Days 3-5). The 12h shift on Day 3 will be achieved by including an 8h wake episode and a 4h sleep opportunity, thereby maintaining the same sleep opportunity-to-wake ratio (1:2). The rationale for the 12h inversion of the sleep-wake timing is that we previously found that the influence of circadian misalignment on physiological variables are maximal when the sleep/wake and fasting/feeding cycle was shifted by ~12h relative to the endogenous circadian timing system. On Test Day 2 (TD2, Circadian misalignment), all subjects will have all the identical tests conducted as described on TD1; however, the FS and start of repeated measures will be at 2100 h – matched to the sleep/wake cycle and not clock time to isolate the impact of circadian misalignment. 24 hours prior to each flexible sigmoidoscopy, stool will be collected from subjects. Discharge from the lab will be on day 7 after an 8h sleep period. We will test for order effects (see Statistics).

**Blood draw.** Blood (30 cc) will be drawn in endotoxin free tube and serum then immediately separated and stored in -80°C freezer until measurement for Serum endotoxin (END). Blood will also be drawn for CBC, comprehensive biochemical profile [CMP that includes

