5. **Minimize the risk of potential side effects associated with in lab stay.** The subject may become sleepy during some segments of the study. The subject will be asked to remain awake during the entirety of their scheduled wake times. Should the subject feel that he/she is unable to remain awake, he/she is free to withdraw his/her consent to participate in this experiment and then go to sleep. At the end of the study, the subject may have difficulty sleeping and waking at their usual times. It may take several days to readjust to their regular routine. This experience is similar to jet lag, and may be associated with upset stomach, insomnia, irritability, or excessive daytime sleepiness. The protocol is designed so that changes in circadian phase are minimized. Subjects may not sleep as well in the laboratory as they do when at home. This may be exacerbated during the simulated night shift when subjects remain continuously awake. Nevertheless, short term partial sleep loss has never been shown to be directly deleterious to health although sleep loss can cause drowsiness and increase the risk of accidents. While dangerous accidents are unlikely in the controlled environment of the laboratory, we have less control when subjects leave the laboratory. Thus, we will ensure that the subject fully appreciates this risk and they will be given the opportunity

to have recovery sleep after completion of the protocol before leaving the laboratory. Taxi rides are arranged so that subjects can return home safely.

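### The Aim 1 power statement is tied to a before/after change in phase angle within UC that the design makes near-certain, while the UC-versus-control difference in change has no stated power

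*Combined protocol and SAP*

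**What the plan says.** - **Hypothesis.** The Abstract sets out to test whether "UC patients (compared to healthy subject controls) are less resilient to circadian misalignment". Specific Aims, Aim 1, has two parts: misalignment is more prevalent in UC than in healthy controls, and UC patients are more susceptible to it.
- **Endpoint.** Study Outcomes makes phase angle the Aim 1 primary outcome, defined as the difference between DLMO and sleep onset. Figure 1 lists it at baseline and at misalignment, with the test given only as ANOVA.
- **Manipulation.** Under Procedures, on Protocol Day 3 "subject behavioral cycles will be shifted by 12h", in all subjects, and the new schedule is held until Day 7. Minimizing Risk, item 5, adds: "The protocol is designed so that changes in circadian phase are minimized".
- **Power.** In the Sample Size Analysis, "we assume a Type I error rate of 0.05 and a 2-sided test for all analyses". The Aim 1 effect is described as roughly a 2 "h phase advance in DLMO in NW compared to DW", with means and SDs of "0.2 (SD=2.1) compared to -4.34 (SD=3.8), respectively" (the first mean carries a minus sign in the plan: -0.2). "With a sample size of 20 in each group (10 men/10 women), this" is said to give 86% power, or 98% with sex pooled. After the Aim 2 figures, the section concludes that these estimates describe the power for "differences in phase angle and colonic permeability between UC patients before and after simulated night shifts".

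**The concern.** Phase angle has two terms. The protocol moves one of them, sleep onset, by 12 h in everyone and is meant to leave the other, DLMO, nearly where it was. A large change from the first test day (TD1) to the second (TD2) is therefore expected in every subject, with or without UC. It confirms that the manipulation worked. It does not show whether UC patients adapt less well than controls.

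The closing power sentence nevertheless attaches the sample-size justification to this change within UC, and no power is tied to the UC-HC difference in change. Two misreadings could follow. A near-certain p-value in UC could be presented as evidence of susceptibility. A non-significant UC-HC comparison could be read as equal resilience because the study was thought to have 98% power.

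**Working it through.** **1. The plan's own figures.** Inputs from the Sample Size Analysis: means -0.2 and -4.34, SDs 2.1 and 3.8 (taken as hours), two-sided alpha 0.05.

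- Difference: -0.2 - (-4.34) = 4.14 h.
- Root-mean-square SD: sqrt((2.1² + 3.8²)/2) = 3.07 h, so d = 4.14/3.07 = 1.35.
- Two independent groups, normal approximation, power = Φ(d·sqrt(n/2) - 1.96). For n = 10: Φ(3.02 - 1.96) = 85.4%. For n = 20: Φ(4.26 - 1.96) = 98.9%.
- Noncentral t: 81.4% and 98.6%.

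The stated 86% and 98% are thus two-group figures. A paired calculation with 3.07 h as the SD of change would give 96.5% (n = 10) and 99.99% (n = 20), which do not match. The two means differ by 4.14 h although the text says about 2 h; at 2 h and SD 3.07 h, 20 per group gives 52%.

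**2. The before/after test of phase angle within UC.** Let D be the movement of DLMO towards the new schedule. The mean change is then 12 - D hours and t ≈ (12 - D)/(SD/sqrt(n)). The documents give neither D nor the SD of change. I assume D from 0 to 6 h and an SD up to 3.8·sqrt(2) = 5.37 h (two uncorrelated measurements with SD 3.8 h).

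| D | SD of change | n | t | Power |
|---|---|---|---|---|
| 0 h | 3.07 h | 20 | 17.5 | >99.99% |
| 0 h | 5.37 h | 14 | 8.4 | >99.99% |
| 6 h | 5.37 h | 20 | 5.0 | 99.7% |
| 6 h | 5.37 h | 14 | 4.2 | 97% |

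The choice of n = 14 is explained in step 4.

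**3. Does that test carry information on resilience?** UC and HC were simulated as equally resilient, with 20 per group, D = 1, 2 or 4 h, SD 2.1 to 5.37 h and 20,000 runs per setting. The before/after test rejected in 100% of runs in UC and in 100% in HC. The UC-HC test of change rejected in about 5%, its nominal level.

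**4. Power for the contrast that matches the hypothesis.** Two-sample t-test on individual changes, with noncentrality (difference/SD)·sqrt(n/2). The SD of change equals SD·sqrt(2(1 - r)), where r is the within-person correlation, so it equals the SD of a single measurement when r = 0.5. I assume 2.1, 3.07 and 3.8 h. With 20 per group:

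| UC-HC difference in change | SD 2.1 h | SD 3.07 h | SD 3.8 h |
|---|---|---|---|
| 1 h | 31% | 17% | 13% |
| 2 h | 84% | 52% | 37% |
| 3 h | 99% | 85% | 68% |
| Smallest difference with 80% power | 1.9 h | 2.8 h | 3.5 h |

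The last row is 0.909 × SD. At SD 3.07 h, a 2 h difference needs about 37 to 38 per group for 80% power: 2(1.96 + 0.84)²·3.07²/2² ≈ 37, and 38 with the t distribution.

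Subject Recruitment reports that 70% of those who pass screening complete the study. If that applied to the 20 per group and dropouts were not replaced, 0.70 × 20 = 14 per group would remain. The smallest difference with 80% power, 1.10 × SD, would then be 2.3, 3.4 and 4.2 h.

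**The case against.** **The calculation is a two-group calculation on DLMO, which the shift in sleep does not force.** This stands. A reader might infer that the 86% and 98% were computed for the within-UC test; step 1 shows they were not. But the two groups are night and day workers, and the input is a difference in DLMO level. It is the plan's closing sentence that assigns the figures to UC before versus after.

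**At an SD of change of 3.07 h, the same arithmetic gives about 98% for a 4.14 h UC-HC difference in change.** Numerically true. The plan does not make that claim, gives no SD of change, and offers no reason why UC and controls should differ in response by as much as night and day workers differ in level.

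**ANOVA over two groups and two conditions can carry the interaction.** It can. A reader might infer that the Aim 1 test will be the before/after test in UC, so that the study cannot answer its question. The documents do not support that: Figure 1 leaves the term unspecified. The defect is in what is named and powered.

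**The 12 h change is not exact.** Also right. Minimizing Risk gives no figure for DLMO movement and expects poorer sleep in the laboratory. A change of exactly 12 h, or a strictly guaranteed result, goes too far; near-certainty over the range in step 2 is what can be said.

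**Permeability is in the same sentence.** The 12 h shift does not force permeability, and Aim 2 asks about the effect of misalignment in UC. The argument covers phase angle only.

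**Conclusion.** The point holds for phase angle. The before/after contrast within UC, to which the plan attaches its Aim 1 power, is a manipulation check. Its power is at least 97% with 14 to 20 subjects, even if DLMO moves 6 h and the SD of change is 5.4 h, and it is uninformative about UC relative to HC. The UC-HC difference in change, which is the susceptibility hypothesis, is neither written out as a test nor powered. With 20 per group its power for a 2 h difference runs from 84% down to 37% over the assumed SDs, so the stated 98% should not be read as describing it.

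This rests on three assumptions: DLMO moves well short of 12 h, as the protocol intends; the SD of change lies between 2.1 and 3.8 h; and, for the 14-per-group figures only, the 70% completion rate applies without replacement. The baseline UC-HC comparison for the prevalence part of Aim 1 is unaffected by the shift.

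**What to change.** 1. State that the Aim 1 susceptibility test is the group-by-condition contrast: the UC-HC difference in change from TD1 to TD2. Express it as DLMO shift, or as change in phase angle with a fixed sign convention. Change in phase angle equals DLMO shift minus shift in sleep onset, so the two agree (apart from the constant 12 h) only if sleep onset follows the imposed schedule. The convention matters near 12 h: DLMO shifts of +1 h and -1 h give -11 h and -13 h, and -13 h reads as +11 h on a 24 h clock.
2. Keep the baseline UC-HC comparison of phase angle for the prevalence part of Aim 1.
3. Remove phase angle, but not permeability, from the before/after-in-UC power sentence.
4. Restate power for the UC-HC difference in change over a range of SDs, as in the table in step 4, and say whether 20 per group means enrolled or completed. Reconcile the 2 h in the text with the 4.14 h between the means.

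The cost is wording in the Sample Size Analysis and Figure 1, and a less favourable power statement. No new endpoint is needed, because phase angle already requires DLMO at both assessments. Whether the melatonin sampling window, which moves with the sleep/wake cycle at TD2, still captures DLMO is a separate question that affects phase angle and DLMO shift alike.
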